## 6.2 SECONDARY EFFICACY ENDPOINTS AND ANALYSES

If the primary efficacy analysis demonstrates non-inferiority, the following key secondary efficacy analyses will be performed at the same timepoint in the ITT analysis set using a fixed sequence testing procedure to control the overall level of significance. Thus, the results of a given key secondary analysis will be considered confirmatory only if the results of all previous tests are successful based on the use of a two-sided test at the alpha=0.05 level of significance. However, once a non-successful result is obtained, all subsequent results will be considered as exploratory rather than confirmatory. The key secondary analyses are the following:

- Superiority analysis of the time to loss of Secondary Patency using the same statistical approach as specified for the primary analysis, except that a two-sided superiority test will be performed,
- Non-inferiority analysis of the time to loss of Primary Patency using the same statistical approach and non-inferiority margin as specified for the primary analysis, and
- Superiority analysis of the time to loss of Primary Patency using the same statistical approach as specified for the primary analysis, except that a two-sided superiority test will be performed.

In order to provide descriptive summary statistics that are of interest, point estimates and 95% confidence intervals for patency (Primary, Primary Assisted and Secondary) survival probabilities will be provided for each group at 6, 12, 18, and 24 months. These estimates will be computed from Kaplan-Meier survival curves for each treatment group for each of the endpoints. For subjects who discontinue early or who complete without meeting criteria for the event, the time-to-event will be censored and defined as the number of days from randomization to the subject's last visit during the study.

Other secondary endpoints to be analyzed include:

- Interventions required that successfully achieved/maintained Secondary Patency. Interventions include whatever is done at one session. For example, thrombectomy + angioplasty at one session would be considered as 1 intervention. Summaries will include:
  - Proportion of subjects who had at least one intervention
  - Number of interventions per subject
  - Distribution of how many had 1, 2, 3... interventions
  - Rate of interventions defined as the number of interventions per subject per year while the conduit is patent (i.e. has not been abandoned). Results will be provided for Day 0 to Month 18 and overall (Day 0 to total follow-up period). Intervention rate for each 6-month interval will be reported.
  - The rate of interventions (number of interventions per 100 person-years) in the two arms will be compared using a Poisson regression model with treatment group and the surgical placement stratification variable as factors, if no overdispersion is present. Otherwise, a negative binomial regression will be used to adjust for overdispersion.
  - The number and rate of thrombectomies, angioplasties and revisions will be analyzed separately
- Interventions that failed to maintain/restore Secondary Patency. In the case when a delayed decision is made to abandon the study conduit (e.g. delayed and then failed thrombectomy), the date of abandonment is back dated to the initial recognition of the thrombosis. Any interventions performed after this date of abandonment will then be considered to have failed to maintain/restore Secondary Patency. Summaries for these interventions will include:
  - Proportion of subjects who had at least one failed intervention
  - Number of failed interventions per subject
  - Distribution of how many had 1, 2, 3 ... failed interventions

- Superiority analysis of the time to loss of Primary Assisted Patency using log-rank test at the 0.05 significance level and similar censoring rules discussed for the primary endpoint.
- Histology assessments of any conduits will be summarized descriptively. Summaries will include the following:
  - The proportion of subjects in whom a sample has been collected
  - The histological findings in each arm will be described and listed
- Dialysis efficiency as assessed by spKt/Vurea (obtained from dialysis unit for a subset of subjects) will be summarized descriptively. The most recent available data prior to the study visits will be used for the analysis.

All secondary endpoints will be summarized by treatment group using counts and percentages for the categorical variables, and n, mean, median, standard deviations, minimum and maximum for the continuous endpoints.

All secondary analyses will occur after all subjects complete at least 18 months post implantation.

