10.3.4 Additional Efficacy Analyses

In order to provide descriptive summary statistics that are of interest, point estimates and 95% confidence intervals for patency (Primary, Primary Assisted and Secondary) survival probabilities will be provided for each group at 6, 12, 18, and 24 months. These estimates will be computed from Kaplan-Meier survival curves for each treatment group for each of the endpoints.

In the primary and key secondary analyses of Primary Patency and Secondary Patency, death will be treated as a censored outcome. These analyses will be repeated as supportive analyses with death treated as an event. Additionally, a time to event analysis will be conducted for all censored subjects and any subjects who withdraw for any reason.

The rates of interventions (number of interventions per 100 person-years) in the two arms will be compared using a Poisson regression model with treatment group and the randomization stratification variable as factors.

Secondary endpoints that are defined as time-to-event variables will be summarized using the Kaplan-Meier method and analyzed using the log-rank test. Proportion endpoints will be analyzed using Pearson's chi-square test and all other quantitative endpoints will be analyzed using the two-sample t-test.

All secondary analyses that are superiority comparisons will be carried out using two-sided tests at the alpha=0.05 level of significance, with no adjustment for multiplicity.

Any analysis of histopathological remodeling on any study conduit will be descriptive only.

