### 3 INVESTIGATIONAL PLAN

#### 3.1 STUDY DESIGN

This is a prospective, multicenter, multinational, open-label, randomized, two-arm, comparative phase 3 study. Approximately 35 sites in the US, Europe and Israel are planned for the study. Subjects who continue to meet inclusion and exclusion criteria on the day of surgery will be randomized in a 1:1 ratio to receive either the HAV or the ePTFE graft during surgery. The randomization will use a block size of 4 subjects and will be stratified by the upper arm or forearm placement. Subjects are considered enrolled at the time of completed informed consent. At least 350 subjects with implanted study conduits [175 with Human Acellular Vessel (HAV), 175 with an expanded polytetrafluoroethylene graft (ePTFE)] are planned to be enrolled in the study.

All enrolled subjects will be followed by study specific visits until the subject completes 2 years (24 months) of follow-up after implantation (irrespective of patency status).

After 2 years, only subjects with a patent conduit will continue to be followed (while the study conduit remains patent) for up to 5 years (60 months) post-implantation or until conduit abandonment (loss of Secondary Patency) at routine study visits. The expected duration of the clinical investigation is 76 months from the initiation of enrollment through the completion of data collection. See Appendix 1 of the study protocol for details of the schedule assessments.

A Data Monitoring Committee (DMC) will be established to review safety on an ongoing basis and to provide recommendations about stopping, continuing or otherwise modifying the study. The DMC will review data unblinded by treatment group and will consist of individuals who are not directly involved in the conduct of the study. As part of their oversight of study conduct, the DMC will review the pattern of interventions and abandonments between treatment groups overall and by study site to assess whether the management of access complications is similar in the two treatment groups.

A separate charter will be established that will describe the roles and responsibilities of the DMC. Responsibilities of the DMC will include review of aggregate safety data from other studies in the HAV clinical development program.

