### 3.2.1 Treatment Arm Assignment

At least 350 subjects who meet inclusion/exclusion criteria will be randomized in the study across multiple investigative sites. Study site personnel will randomize the subject utilizing a voice- or web-based randomization system to either HAV or ePTFE during surgery (i.e., after the surgical site [upper- vs fore-arm] has been selected and after confirmation that the subject is not a candidate for creation of an autologous AV fistula). Randomization may only occur once the arterial and venous exposures have been completed with confirmation of adequate arterial inflow and venous outflow. The randomization schema will ensure that subjects will be randomly assigned in a 1:1 ratio to the HAV or ePTFE arms of the study.

The randomization will be stratified by country (6 planned: US, Poland, Israel, Germany, UK and Portugal) and the upper arm or forearm placement based on the Investigator's determination of where the study conduit should be located. A blocked randomization of size 4 will be used. Subjects are considered enrolled at the time of completed informed consent. Country will not be included as a stratification variable for the statistical analysis for effect, but is only included in the randomization scheme to ensure a balance of treatment groups in each country.

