Unless otherwise specified, continuous variables will be summarized by presenting the number of non-missing observations, mean, standard deviation, median, inter-quartile range, minimum and maximum. Categorical variables will be summarized by presenting the number of subjects and percentage for each category.

Unless otherwise noted, all tests of treatment effects will be conducted at a 2-sided alpha level of 0.05 and two-sided 95% confidence intervals (CI) will be calculated. All tests of interactions between treatment groups and other factors will be conducted at a 2-sided alpha level of 0.10, unless otherwise noted. Parametric and nonparametric methods, as determined by the distribution of each variable, will be used to test statistical hypotheses of continuous variables. In the event of highly skewed data, a logarithmic transformation will be considered prior to any statistical testing.

All p-values will be rounded to 3 decimal places. A p-value rounded to 1.000 will be displayed as >0.999, and a p-value rounded to 0.000 will be displayed as <0.001.

Multiplicity will be managed by testing the primary and key secondary endpoints in a hierarchical fashion. All analyses will be performed using data pooled across sites.

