The hazard ratio (HAV relative to ePTFE graft) will be estimated using a Cox proportional hazards regression with treatment group and the surgical placement stratification variable as factors. Based on the estimated event-free rate in the ePTFE graft arm at the data cut-off using Kaplan-Meier method, the non-inferiority margin will be determined by the hazard ratio corresponding to a difference of 10 percentage points. Hazard Ratio (HAV to ePTFE) Margin = $\text{Log}(\text{ePTFE K-M estimated event free rate} - 0.1) / \text{Log}(\text{ePTFE K-M estimated event free rate})$ . For analyses conducted at 12 months, the hazard ratio will be calculated from the ePTFE K-M estimated event-free rate at 12 months. For analyses conducted at 18 months, the hazard ratio will be calculated from the ePTFE K-M estimated event-free rate at 18 months. Similarly, for analyses conducted at 24 months, the hazard ratio will be calculated from the ePTFE K-M estimated event-free rate at 24 months. If the upper limit of the two-sided 95% confidence interval for the hazard ratio is less than the corresponding non-inferiority margin hazard ratio, then non-inferiority will be demonstrated.

The primary analysis will be in the ITT analysis set. The analysis of the primary endpoints of interest will be repeated using the mITT and per-protocol analyses sets as confirmatory.

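### The log-rank test for Primary Assisted Patency names no stratum although randomisation is stratified by arm location; stratifying it would cost almost nothing and could recover some power

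*SAP*

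**What the plan says.** SAP 6.2 lists, among the other secondary endpoints, a "Superiority analysis of the time to loss of Primary Assisted Patency using log-rank test at the 0.05 significance level", with censoring rules similar to those of the primary endpoint. Protocol 10.3.4 sets the general rule: "Secondary endpoints that are defined as time-to-event variables will be summarized using the Kaplan-Meier method and analyzed using the log-rank test". Neither sentence names a stratum or a covariate, and neither uses the word unstratified. Under SAP 4 the test is two-sided ("all tests of treatment effects will be conducted at a 2-sided alpha level of 0.05").

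On the design, SAP 3.1 states: "The randomization will use a block size of 4 subjects and will be stratified by the upper arm or forearm placement". SAP 3.2.1 adds country as a randomisation factor and then excludes it from the analysis: "Country will not be included as a stratification variable for the statistical analysis for effect". It makes no such exclusion for arm location.

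On the neighbouring analyses:
- SAP 6.1 estimates the treatment effect on Secondary Patency with a "Cox proportional hazards regression with treatment group and the surgical placement stratification variable as factors", and SAP 6.2 carries that approach over to Primary Patency.
- SAP 6.2 compares intervention rates with a "Poisson regression model with treatment group and the surgical placement stratification variable as factors", switching to negative binomial regression if there is overdispersion. The access-related infection analysis in SAP 7.2 uses the same factors.

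**The concern.** Stratified randomisation balances upper-arm and forearm placements between the treatment groups. If placement predicts loss of patency, a log-rank test that ignores it suffers in two ways. Its variance allows for chance imbalance in placement that the design has largely removed, so the test falls below its nominal size. Pooling strata with different hazards also pulls the apparent treatment effect towards the null, because high-risk conduits fail early and leave the risk set. Both effects reduce power.

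At stake are some sensitivity on one secondary endpoint and clarity of specification. Two programmers could read the same SAP sentence and produce different p-values. Primary Assisted Patency would also be handled differently from the two patency endpoints it is read alongside, with no reason given.

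**Working it through.** **The plan's nearest figure.** The documents give no power, effect size or event count for Primary Assisted Patency. The closest stated figure is 90% superiority power for Secondary Patency with 350 subjects and 12-month event-free rates of 60% and 76% (Protocol 10.5, SAP 11).
- Hazard ratio: ln(0.76)/ln(0.60) = 0.537.
- Events, with every subject followed for 12 months: 175 × 0.40 + 175 × 0.24 = 112.
- Schoenfeld power: Φ(√112/2 × |ln 0.537| − 1.96) = 0.908.

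This matches the stated 90%. With 16 months of accrual and 12 months' minimum follow-up, the same formula gives about 162.5 events and 0.977. Nothing below depends on which variant was used.

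**Inputs from the documents.** 350 subjects, 1:1, blocks of 4 within location; 16-month accrual; at least 18 months' follow-up at the secondary analyses (SAP 6.2); deaths of about 20% per year, treated as censoring (SAP 6.1); two-sided 0.05.

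**Inputs assumed, because the documents give none.** Location hazard ratio 1 to 3; split between locations 50:50, or 25:75 with the quarter at higher risk; treatment hazard ratio 0.67; exponential event times; control 12-month event-free rate of 50% at the geometric mean of the two location hazards.

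**Statistics compared.** With U the sum over event times of observed minus expected events in one arm, and V its hypergeometric variance:
- plain: Z = U/√V, computed on all subjects together;
- stratified: Z = (U₁ + U₂)/√(V₁ + V₂), computed within each location and then summed.

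Each rejects when |Z| > 1.96. There were 15,000 simulated trials per scenario.

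| Location HR | Plain power, 50:50 | Stratified power, 50:50 | Gain, 50:50 (points) | Gain, 25:75 (points) |
|---|---|---|---|---|
| 1.0 | 81.4% | 81.3% | −0.1 | −0.2 |
| 1.25 | 80.9% | 81.0% | 0.0 | +0.2 |
| 1.5 | 80.4% | 81.5% | +1.1 | +0.7 |
| 2 | 78.6% | 81.6% | +3.1 | +2.4 |
| 3 | 71.1% | 80.0% | +8.9 | +6.9 |

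Gains come from paired, unrounded results. Their Monte Carlo standard error is at most 0.3 points.

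**Size with no treatment effect, 50:50 split.**

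| Location HR | Plain | Stratified |
|---|---|---|
| 1.0 | 0.050 | 0.049 |
| 1.5 | 0.047 | 0.051 |
| 2 | 0.042 | 0.051 |
| 3 | 0.032 | 0.049 |

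**Sensitivity to the other assumptions.** At a treatment hazard ratio of 0.70 and a control 12-month event-free rate of 60% (6,000 trials), the gain was between −0.5 and +0.3 points at location hazard ratios of 1 to 1.25. It was 0.8 to 0.9 at 1.5, and 2.4 to 3.2 at 2. A further set at treatment hazard ratio 0.70 (4,000 trials) gave essentially no gain at 1 to 1.25, about 1 point at 1.5, 3 to 5 points at 2 and 9 to 11 points at 3. The plain test's size there was about 4.3% at a location hazard ratio of 2 and 3.3% at 3. Higher event rates widen the gap.

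Across all sets the gain from stratifying is therefore about 0 points at 1 to 1.25, 1 at 1.5, 2 to 5 at 2 and 7 to 11 at 3.

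**The case against.** The strongest reply is that little rests on this test. Primary Assisted Patency is an other secondary endpoint, outside the fixed sequence and absent from the sample-size section. Protocol 10.3.4 applies no multiplicity correction to superiority tests of this kind. The SAP follows the protocol, so the two do not conflict, and a simpler test for a lower-tier endpoint is defensible. An analysis need not mirror every randomisation factor either, since country is left out on purpose. Nor is this the only analysis without a named location factor: the 24-month restricted-mean analyses in SAP 6.1.1 name none. All of this stands. It limits the weight of the point but does not remove the gain. Country is omitted with a stated reason; location has no such statement.

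Three stronger readings are tempting, and the documents do not support them.
- *A reader might infer that the plan prescribes an unstratified test.* It is silent; the plain test is only the natural reading.
- *A reader might infer that power is certainly being lost.* That requires location to predict patency, on which the documents give no figure.
- *A reader might infer that the test is invalid.* Under stratified randomisation the plain log-rank errs on the conservative side, and no excess of false positives is shown.

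Timing is a fair objection too. The current SAP text postdates version 5.0 of 01 May 2019. On the planned dates, a start in the second quarter of 2016 plus 16 months' enrolment plus 18 months' follow-up is 34 months, which ends in early to mid 2019. The 18-month data may therefore have been seen in an open-label trial. This is inferred from planned dates, and the fix allows for it.

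**Conclusion.** The point holds as a minor, optional improvement. The documents leave the form of the test unstated, and its natural reading departs from the models used for the other patency endpoints and for the rates. The benefit of stratifying runs from nothing to 11 points of power over assumed location hazard ratios of 1 to 3, and it is 5 points or less up to a hazard ratio of 2. Those figures rest on the assumed location effect, split, treatment effect and event rate; none of these is given for this endpoint. The direction does not depend on the exact values: there is essentially no gain when location is not prognostic, and the gain rises as location matters more. The trial's confirmatory conclusions are untouched.

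**What to change.** In SAP 6.2, name the test as a log-rank test stratified by randomised (intended) surgical placement, upper arm or forearm. Intended placement matches the rule that SAP 4.2 already sets for the ITT analysis set. Align the wording of Protocol 10.3.4 at its next revision; a separate amendment for this alone is not needed. If 18-month data have already been seen, date the change and report the unstratified result next to the stratified one. If the sponsor prefers the plain test, the SAP should say so explicitly.

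The cost is one phrase in the SAP and one stratum term in the program. If location is not prognostic, the statistical cost is a fraction of a point of power (0.1 to 0.2 points in the 15,000-trial simulations).

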3.2 Secondary Objectives

3.2.1 Key Secondary Objectives:

Efficacy

To compare the Primary Patency of the HAV with that of the ePTFE graft.

Safety

To compare the rate of access-related infections for the HAV with that of the ePTFE graft.

3.2.2 Other Secondary Objectives:

Efficacy

1. To compare the rate of interventions needed to maintain/restore patency of the HAV with that of the ePTFE graft.
2. To compare the Primary Assisted Patency of the HAV with that of the ePTFE graft.
3. To describe the histopathological remodeling of samples from HAV and ePTFE grafts.
4. To compare the efficiency of dialysis with the HAV with that of the ePTFE graft in a subset of subjects.

Safety

1. To compare the safety and tolerability of the HAV with that of the ePTFE.
2. To compare the relative rates of true aneurysm and pseudo-aneurysm formation.

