8.5.1.8 Assessment of Adverse Events

The subject will be asked general questions about his/her health and for any conduit or dialysis problems since the previous visit. See [Section 9](#) for information regarding AE collection and data handling.

8.5.2 Evaluations and Procedures to be performed only at Specific Visits from Month 2 to Month 24

8.5.2.1 Duplex Ultrasound: Month 2, 3, 6, 12, 18 and 24

A duplex ultrasound will be performed to assess study conduit patency, diameter of the lumen mid-conduit, implant and anastomotic stenosis, volumetric flow rate, and to monitor for aneurysm development. The full length of the study conduit should be visualized with particular attention paid to any increase in diameter of the conduit that might indicate aneurysm formation.

8.5.2.2 Document Removal of CVC that was in place Pre-randomization: Month 2 and 3

Record the date and reason for removal of the CVC that was in place pre-randomization, if applicable.

8.5.2.3 Additional Data from Dialysis Unit: Month 3, 6, 12, 18 and 24

For a subset of subjects, the CRO will obtain, via data transfers from dialysis organizations, the following data obtained at a time closest but prior to the study visit (these data will be obtained from labs drawn at the discretion of the dialysis unit; where feasible and appropriate, these data will be obtained prior to study conduit implantation, too):

- $\text{spKt}/V_{\text{urea}}$ (to enable assessment of dialysis efficiency)
- Hemoglobin
- Erythropoiesis-stimulating agent (ESA) used and dose
- HbA1c (last value prior to study conduit implantation only)

8.5.2.4 PRA: Month 6, 12, 18 and 24

PRA samples will be drawn at Month 6, 12, 18, and 24. PRA samples should also be drawn prior to transplantation for any subjects who receive a transplant during the study.

8.5.2.5 Laboratory Data: Month 6, 12, 18 and 24

At Month 6, 12, 18 and 24, a blood sample will be collected for the following:

- Hematology: hemoglobin, hematocrit, RBC, WBC with differential, platelet count.
- Clinical chemistry: sodium, potassium, calcium, BUN or urea, creatinine, albumin, total bilirubin, ALT, AST, alkaline phosphatase, glucose (non-fasting)

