#### 2.2.0.2 ***Other Secondary Efficacy Endpoints***

- Rate of interventions required to achieve/maintain Secondary Patency
- Time to loss of Primary Assisted Patency from implantation. Primary Assisted Patency is defined as ‘the interval from the time of access placement until access thrombosis or the time of measurement of patency, including intervening manipulations (surgical or endovascular interventions) designed to maintain the functionality of patent access’ i.e., patent without an intervention to clear a thrombus ([Sidawy 2002](#))
- Histopathological remodeling of any study conduit (based on samples collected)
- The efficiency of dialysis as assessed by spKt/Vurea (obtained from dialysis unit for a subset of subjects)

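### Comparing dialysis efficiency between arms is a stated objective and the protocol assigns a t-test, but the SAP only summarizes spKt/Vurea by arm and pre-specifies no difference or confidence interval

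*SAP*

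**What the plan says.** The objective is comparative. Protocol 3.2.2 has: "To compare the efficiency of dialysis with the HAV with that of the ePTFE graft in a subset of subjects". The SAP repeats it under Other Secondary Efficacy Objectives in Section 2.1. In both lists the neighbouring histopathology objective is to describe, not to compare.

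Protocol 10.3.4 gives the method through a general rule: "all other quantitative endpoints will be analyzed using the two-sample t-test". Secondary superiority comparisons use "two-sided tests at the alpha=0.05 level of significance, with no adjustment for multiplicity". The one efficacy endpoint exempted from testing there is histology: "Any analysis of histopathological remodeling on any study conduit will be descriptive only".

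SAP 6.2 treats spKt/Vurea differently: "Dialysis efficiency as assessed by spKt/Vurea (obtained from dialysis unit for a subset of subjects) will be summarized descriptively". Its format rule begins "All secondary endpoints will be summarized by treatment group using counts and percentages for the categorical variables" and adds n, mean, median, SD, minimum and maximum for continuous endpoints. SAP 4.4 takes the latest value before each study visit.

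Protocol 8.5.2.3 schedules the transfers at Months 3, 6, 12, 18 and 24 and adds: "where feasible and appropriate, these data will be obtained prior to study conduit implantation, too".

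**The concern.** An objective worded as a comparison should lead to a planned contrast: a difference, its uncertainty, and the visit or visits at which it is read. Here the protocol names a test and the SAP drops it, and neither document gives a reason.

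Followed as written, the SAP yields two columns of means at up to five visits. A reader would compare them by eye, or choose a visit and compute a difference after seeing the data. The values come from dialysis organizations for a subset, and neither document describes random selection of that subset. That makes a contrast chosen after the fact harder to defend.

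**Working it through.** **1. The two plans side by side.** Neither document states a sample size, SD, effect size or power for spKt/Vurea, so there is no figure to reproduce. The check is textual.

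| Item | Protocol | SAP |
|---|---|---|
| Objective | Compare, in a subset (3.2.2) | Compare, in a subset (2.1) |
| Method for spKt/Vurea | Two-sample t-test, by the general rule (10.3.4) | Descriptive summary by arm (6.2) |
| Descriptive only | Histopathology (10.3.4) | Histology and spKt/Vurea (6.2) |
| Visit for the contrast | None named | No contrast |
| Pre-implantation value | Obtained where feasible (8.5.2.3) | Baseline defined generally (4.6); no use specified for this endpoint |

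**2. Whether the omission is general or specific.** SAP 6.2 names between-arm methods for other secondary endpoints: Poisson or negative binomial regression for intervention rates, and the log-rank test for Primary Assisted Patency. The missing contrast is therefore not a policy for all such endpoints. The SAP revision tables record removal of a chi-square comparison from 6.2 but do not mention a t-test for spKt/Vurea.

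**3. What the planned tables allow.** With n, mean and SD per arm, a reader can form the unadjusted contrast at any visit:

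- difference = mean(HAV) − mean(ePTFE)
- SE = s × √(1/n₁ + 1/n₂), with s the pooled SD

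So a crude estimate can be recovered, but it is not planned.

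**4. Likely precision (assumed n per arm, equal arms).** Half-width of the 95% CI in SD units = t(0.975, 2n−2) × √(2/n):

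- n = 25: 0.57
- n = 50: 0.40
- n = 100: 0.28
- n = 175 (the planned arm size, so every subject): 0.21

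**5. Effect of the pre-implantation value (assumed correlation r with follow-up).** If every analysed subject had one, the half-width would be multiplied by √(1−r²):

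- r = 0.3: √0.91 = 0.95
- r = 0.5: √0.75 = 0.87
- r = 0.7: √0.51 = 0.71

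At n = 50 the half-width of 0.40 would become 0.38, 0.34 or 0.28. The documents give neither r nor the share of subjects with a value. Inclusion criterion 2 admits subjects not yet on hemodialysis, who cannot have one.

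**6. How that value must enter a model.** Suppose it is a sixth response and the model has one common arm term. With complete data and compound symmetry, the arm estimate is the difference in six-visit averages. A constant post-implantation effect δ, absent before implantation, is then estimated as (0 + 5δ)/6 = 0.83δ, a loss of one sixth. Separate arm terms at each post-implantation visit, with arm means equal before implantation, avoid this.

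**The case against.** The best defence has four parts.

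- **The t-test comes from a catch-all.** It does not name spKt/Vurea, and Protocol 10 leaves further detail to the SAP. But spKt/Vurea is a quantitative efficacy endpoint, and the protocol's only efficacy exemption is histopathology, so the rule covers it.
- **The SAP allows for changes.** Section 4 lets changes that do not alter a principal feature be justified in the clinical study report, and it has general language on testing continuous variables. The first defers the explanation. The second names no test or estimate for this endpoint and yields to the specific wording in 6.2.
- **The data are opportunistic.** Values are drawn at the dialysis unit's discretion. Subjects are followed to 24 months whether or not the conduit is patent, and other dialysis routes may be in use. A between-arm difference could therefore mix accesses. This stands as a caution on interpretation. It applies equally to the planned arm means, and it supports an exploratory label rather than no contrast.
- **The endpoint is minor.** This stands.

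A reader might go further and infer that the SAP leaves the objective unanswerable. It does not, because the planned summaries allow a crude difference. Nor does the missing estimate come from leaving out the pre-implantation value. Neither document promises baseline adjustment, and the protocol's own t-test is unadjusted, so using the value is an optional gain in precision. It is also tempting to assume few values per visit, but no count is given.

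**Conclusion.** The inconsistency is real and its consequence is small. A declared comparison has a test in the protocol and only per-arm description in the SAP, so no between-arm difference or confidence interval is pre-specified. The endpoint lies outside the fixed testing sequence, and neither the primary conclusion nor the key secondary tests are affected. Correcting it would be a worthwhile improvement, not a necessity.

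This rests on reading the protocol's general rule as covering spKt/Vurea, which its wording supports. The half-widths and multipliers above illustrate assumed subset sizes and correlations. They are not properties of this trial.

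**What to change.** In SAP 6.2, report the HAV minus ePTFE mean difference in spKt/Vurea with a nominal 95% CI at each of Months 3, 6, 12, 18 and 24. Align Protocol 10.3.4 so that both documents name the same analysis.

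A suitable model is a repeated-measures model with visit, arm-by-post-implantation-visit terms and placement stratum. Any available pre-implantation value enters as a response, with arm means constrained equal at that time, and is not also a covariate. Subjects without one are kept. State that the result is exploratory, because it comes from a subset whose random selection is not described.

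If the sponsor prefers description only, the objective should be reworded to describe in both documents and the reason recorded.

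The cost is wording in both documents and one model. The data are already due to be transferred, and Protocol Appendix 1 asks nothing of sites for them. The limitation is that the pre-implantation value will exist for only part of the subset, so its benefit cannot be known in advance.
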